3.3 Investigational Products and Treatments

3.3.1 Treatment Schedule

Each treatment arm is administered and considered active for a period of maximum 8 weeks; the non-invasive treatment is administered for 6 weeks followed by a 2-week “wash-out” period, and the UCB infusion will be followed by supplement administration after an 8-week interval. Patient evaluation, registration informed consent and randomization occur at initial visit 0 (V0); followed after 14-21 days by V1 (longer for the preparation of UCB infusion), during which the first treatment is administered; V2 after another 8 weeks, at which the second treatment is administered, and V3, V4, and V5, at 16, 24 and 52 weeks respectively after V1.

A tabulated summary of the study visits was given above Section 3.1.1

3.3.2 Randomisation

Because it is an open-label study, there is no need for blinding/assigning participant numbers. Each participant will be randomly assigned to begin the study either with the UCB infusion or the non-invasive treatment.

Eligible patients, who for whatever reason, do not report to the clinic to receive the first treatment after having been selected for the study will be referred to as discontinuers in the report. A patient who, for whatever reason, withdraws or is withdrawn from the study after having been enrolled, will be classified as a dropout, and identified as such in the relevant Case Report Form (CRF).

3.3.3 Identity of study Treatments

After receiving it from the storage bank, UCB will be tested for HLA determinants at the National Institute of Hematology laboratory by gene sequencer.

Afterward positive confirmation UCB will be thawed according to the Duke/Rubinstein protocols. A vial containing 1.5 ml thawed UCB will be sent for TNC/viability by flowcitometry at Victor Babes Laboratory. A label with patients' name, date is affixed to each UCB bag prepared for infusion.

Study code: Bio-Forum Foundation001	Visit no:
Investigator: [name] no:
Investigational product: UCB	
Patient name	
Keep at room temperature	Exp Date:
For clinical study use only	

3.3.4 Storage and Accountability

UCB collections will be kept in liquid nitrogen, vapor phase – 170 degrees Celsius - at all times prior to thawing of collection, and there will be periodic recording of this condition. Transport recipients (dry shippers come with temperature sensors, which will be photographed, and during HLA testing, the collection is kept also in liquid nitrogen and its storage at below – 170 degrees Celsius will also be documented via periodic photography of the measuring device.

The Principal Investigator of the study – [name] – is directly responsible for this stage of UCB preparation.

3.3.5 Allowed medication

Preferably no other medicine should be taken by the subjects. The use of any incidental medication (e.g. mild analgesics, NSAID, etc) must be recorded.

3.3.6 Compliance

The parents will attest to the use of study medication on a daily basis and the adherence to the prescribed treatment will be checked at every clinic visit.

4 STUDY MEASUREMENTS AND ENDPOINTS

In this study the following endpoints will be measured/recorded

1. Efficacy - difference in the scores on the questionnaires M-CHAT, Q-CHAT and CAST before and after each treatment

2. Safety – type, severity, duration, treatment and amelioration of each of the adverse effects occurring during respective treatments.

4.1 Primary Safety Endpoints.

–

1. Adverse events (type and frequency)
2. Physical examination parameters (body mass, height, etc)
3. Vital signs: blood pressure, heart rate, respiratory rate, body temperature
4. Laboratory tests
 - HLA testing by genetic sequencing
 - Haematology: CBC - RBC, HB, MCHC, MCH, MCV, RDW, Hct, Hb, WBC Differential count –lymphocytes monocytes, neutrophils, eosinophils, basophils, flowcytometry - CD34+, TNC, viability %
 - Microbiology – presence and sensitivity of pathogens
 - LFTs Serum - Bilirubin (total and conjugated) AST, ALT, GGT, LDH, glucose
 - IP – serum protein electrophoresis, ESR, CRP, fibrinogen
 - Els - sodium, potassium, chloride, calcium, magnesium.

4.2 Measurements at each visit.

See section 3.1.1 for the visit schedule.

Visit 0: Screening Visit

Patients will be examined within 14 days prior to the first ingestion of the investigational products to assess their eligibility to participate. For each child both parents will consent in writing (Appendix 1, Informed Consent Form) to the screening process before the start of the examination. The consent form will also include the study information leaflet.

The examinations and investigations will include:

- Medical history, including history of past use of medications, demographics (date of birth, sex, race) and ASD diagnosis.
- Physical examination including assessment of general appearance, cardiovascular, lungs, mouth, throat and abdomen and measurement of height and body weight. The examination will be made in accordance with the normal clinical routines at the trial center.
- Vital signs: systolic and diastolic blood pressure in supine (after 5 minutes rest) and standing positions (1minute), pulse, respiratory rate and oral temperature.
- Laboratory tests: HLA, Haematology, (see section 4.4.3.2); baseline plasma levels of IP, Els, LFTs (these can be drawn also at V1 if considered by the study PI)

Based on the results of the testing with the M-CHAT-R, Q-CHAT and CAST questionnaires and the evaluation from child psychologist, a recommendation for treatment will be made for either UCB administration or the noninvasive treatment for 6 weeks

Visit 1: The first treatment is administered

- The pre-dose safety assessments and eligibility checks will be recorded on the relevant pages in the individual CRFs.
- The parents will also be given the 3 questionnaires and instructed on how to complete it.
- The parents will be issued with prescriptions for trial medication, explained how to take the medication and given next appointment date; or
- The UCB infusion is administered

Visit 2: Second Treatment is administered

For these visits the examinations and investigations will include:

- Physical examination (as for visit 1)
- Vital signs: systolic and diastolic blood pressure in supine, pulse, respiratory rate and oral temperature.
- Laboratory tests
 - HLA testing by genetic sequencing
 - Haematology: CBC - RBC, HB, MCHC, MCH, MCV, RDW, Hct, Hb, WBC
 - Differential count –lymphocytes monocytes, neutrophils, eosinophils, basophils,
 - flowcytometry - CD34+, TNC, viability %
 - Microbiology – presence and sensitivity of pathogens
 - LFTs Serum - Bilirubin (total and conjugated) AST, ALT, GGT, LDH, glucose
 - IP – serum protein electrophoresis, ESR, CRP, fibrinogen
 - Els - sodium, potassium, chloride, calcium, magnesium.

Note: For any patient in which any of the above tests indicated levels outside the normal range, a follow-up visit (visit A-C) will be scheduled for an appropriate time (1 or 3 months post visit). All or the above tests will be repeated at this visit.

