3.1.1 Scheduled study visits

Recruitment of patients will occur during initial contacts with the study coordinator [name] who will present the parents with the opportunity to enroll in the study, and when general information will be given about the study on timeline, procedures involved, tests, costs.

After agreeing in principle to participate in the study, parents and child will be scheduled for **Visit 0**, at which the patients' blood is drawn for testing, questionnaires are completed, the patient is evaluated by the child therapist and is randomized for receiving treatment A (UCB infusion) or B (noninvasive treatment), and the necessary arrangements are made for UCB release from the respective banking site.

Visit 1 is scheduled within 7-14 days from V0, and during this study visit the child will receive either treatment A or B. Treatment B (noninvasive) is administered daily for 6 weeks, and is followed by 2 weeks with no treatment (washout period)

Visit 2 follows at 8 weeks distance from V1, which includes the 2 week washout period after the first treatment is administered. New blood tests are performed, also questionnaires and evaluation by child therapist, and the other treatment in sequence is administered.

Visit 3, Visit 4, and Visit 5 are scheduled at 16, 24 and 52 weeks after first treatment was administered (V1) and involve the neuropsychological evaluation of the child by the therapist and with the 3 questionnaires; brain imaging is recommended at 52 weeks

	Visit 0	V1	V2 (+ 8 weeks)	V3 (+16 wks)	V4 (+24 wks)	V5 (+52 wks)
Labs	CBC, LFTs, Els, HLA; IP	HLA MB	CBC, LFTs, Els, HLA; IP; MB			
Imagis-tics	MRI/CT					MRI/CT
Neuro/Psi Evaluation	M-CHAT-R; Q-CHAT; CAST; - Child therapist	x	M-CHAT-R; Q-CHAT; CAST; - Child therapist	M-CHAT-R; Q-CHAT; CAST; - Child therapist	M-CHAT-R; Q-CHAT; CAST; - Child therapist	M-CHAT-R; Q-CHAT; CAST; - Child therapist
Treatment started	randomi-zation	A/B	B/A	X	X	X

CBC – complete blood count with differential; LFTs – liver function tests, Els – electrolytes; IP – Inflammatory panel – ex ESR, CRP, serum protein electrophoresis, neopterin, IL-6; HLA – Typing of patient HLA- A, HLA-B, HLA-DR; MB - microbiology

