5 STATISTICAL METHODS

5.1 Determination of sample size

Based on literature we expect that a sample size of minimum 25 participants will be needed in order to observe an alpha value of 0.05 (95% probability) with a p value of 0.05 and a power of 80%. ANOVA testing will be performed on the respective groups of patients

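### V2 is the only score between the two treatments, so a child's two before-after changes share it; with no within-child model or persistence assumption stated, the A-B comparison can be wrong

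*Combined protocol and SAP*

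**What the plan says.** All references are to the combined protocol and SAP.

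- **Endpoint (Section 4).** Efficacy is the "difference in the scores on the questionnaires M-CHAT, Q-CHAT and CAST before and after each treatment". The visits that supply 'before' and 'after' are not named.
- **Schedule (Section 3.1.1).** "Visit 2 follows at 8 weeks distance from V1, which includes the 2 week washout period after the first treatment is administered". At that visit: "New blood tests are performed, also questionnaires and evaluation by child therapist, and the other treatment in sequence is administered". V3, V4 and V5 follow at 16, 24 and 52 weeks after V1. Treatment B is given for 6 weeks and then stopped for 2.
- **First baseline.** Questionnaires are completed at V0. Section 4.2 adds for V1: "The parents will also be given the 3 questionnaires and instructed on how to complete it". The schedule table shows only a cross in the V1 cell, so V1 scores are not clearly planned.
- **Duration of effect (Section 3.3.1).** "Each treatment arm is administered and considered active for a period of maximum 8 weeks".
- **Analysis (synopsis and Section 5).** The synopsis names analysis of variance for continuous variables. Section 5.1 says: "ANOVA testing will be performed on the respective groups of patients". Section 5.2 describes baseline and safety analyses and reports means with SEM and 90% limits. It has no efficacy paragraph. No child, period, sequence or carryover term appears anywhere.

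**The concern.** Comparative efficacy is the primary objective (Section 2). The endpoint yields two changes per child, and one measured score, V2, enters the first with a plus sign and the second with a minus sign. This raises two separate questions.

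1. **Precision.** A chance high or low at V2 moves the two changes in opposite directions, so they tend to be negatively correlated. An ANOVA that compares the A changes with the B changes as if they came from different children ignores this and can misstate the standard error of A-B.
2. **Bias.** The V2 'before' score for the second treatment still contains whatever effect the first treatment has at week 8. If that effect then fades, the loss is booked against the second treatment. A paired analysis does not remove this.

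**Working it through.** **Inputs from the documents:** questionnaire visits V0, V2 (week 8) and V3 (week 16); minimum 25 children, optimum 40; alpha 0.05.

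**Assumptions, because the plan is silent:** two-sided test; equal sequences; V3 is the 'after' visit for the second treatment; additive effects.

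**The plan's own figure.** The sample size of 25 cannot be reproduced, because no effect size or SD is given. At 80% power it corresponds to (1.96 + 0.842)/√25 = 0.56 SD of the within-child difference. Nothing below depends on it.

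**Step 1, the contrast.** D1 = V2 − V0 and D2 = V3 − V2, so D1 − D2 = 2·V2 − V0 − V3.

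**Step 2, variance with equal correlations.** Take a child level plus independent visit errors of variance s².
- Var(D1) = Var(D2) = 2s², Cov(D1, D2) = −s², correlation −0.5.
- True Var(D1 − D2) = 6s². Treated as independent: 4s².
- At n = 25 the true SE is √(6/25)·s = 0.490s and the assumed SE is √(4/25)·s = 0.400s. The ratio is 0.816, so the SE is 18% too small.
- Type I error = 2·[1 − Φ(1.96/√1.5)] = 11.0%. Simulations gave 10.3% to 10.7% at n = 25 and 10.9% to 11.1% at n = 40.
- A nominal 90% interval for A-B covers about 82%.

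**Step 3, other correlation structures.**
- Correlation decaying with time (rho between adjacent visits): true over assumed variance is (3 − rho)/2. This is 1.25 at rho = 0.5 and 1.05 at rho = 0.9, giving errors of 8.0% and 5.6%.
- Child-specific trends of SD t per interval: the true variance stays 6s², while the assumed variance is 4s² + 2t². Simulated error at n = 25 is 8.4% for t = 0.5s, about 5% for t = s, and about 2% (conservative) for t = 1.5s.

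**Step 4, what is unaffected.** In simulation the 90% limits of one treatment's own mean change covered 90% in every setting. A paired analysis of the same changes gave 4.6% to 5.3% error.

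**Step 5, expectation of the change contrast.** Let a and b be the effects of A and B on the score 8 weeks after start, and L the share of the first effect still present at V3. Averaged over equal sequences:

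E = (a − b) + 0.5·[(1 − L_A)·a − (1 − L_B)·b]

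| Persistence at V3 | Estimate |
|---|---|
| Both gone (L = 0) | 1.5(a − b) |
| Both half present (L = 0.5) | 1.25(a − b) |
| Both full (L = 1) | 1.0(a − b) |
| A full, B gone | a − 1.5b |

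If V4 were the 'after' visit and both effects had gone by then, the sequences give 2a and −2b, and half their sum is 1.0(a − b).

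**Step 6, direct comparison of V2 and V3 scores.**
- Expectation: (a − b) − 0.5·(L_A·a − L_B·b). This is 1.0(a − b) with L = 0 and 0.5(a − b) with L = 1.
- Variance with equal correlations: 2s², one third of 6s². SE at n = 25 is √(2/25)·s = 0.283s. With decaying correlation the change contrast has 3 − rho times this variance, or 2.1 to 2.5 times for rho from 0.9 to 0.5.
- With L = 0 the signal-to-noise ratio per unit of (a − b)/s is 1/0.283 = 3.54, against 1.5/0.490 = 3.06 for the change contrast. The larger expected estimate does not make up for its larger variance.

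**The case against.** **The plan never says that the changes are treated as independent.** The groups in Section 5.1 could be the sequence groups, and a standard crossover ANOVA with child and period on these same changes is valid: it simulated at 4.9% with a 13:12 split. This stands. A reader might infer that reusing V2 in itself makes every error bar wrong; the documents do not support that. The fault would lie in an unpaired analysis, and the SEMs and 90% limits in Section 5.2 are sound for each treatment's own mean change. What remains is that no within-child model is written down, and the wording that is there permits the invalid one.

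**The factor 1.5 is one case.** A reader might infer that the plan overstates the difference by half. Section 3.3.1 does imply that the first effect is gone by V3, 16 weeks after the first treatment. But it gives 8 weeks as a maximum, V2 falls exactly at week 8, and B has by then been stopped for 2 weeks. A full effect at V2 is therefore not established, and with no effect left there is nothing to multiply. Nor is it right that the factor is 1.0 only under full persistence: with a = 1, b = 0.5, half of A and none of B left at V3, the estimate is 0.5 + 0.5·(0.5 − 0.5) = 0.5, the true difference.

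**The direct comparison carries its own assumption.** This also stands. If only A persists, with a = 1 and b = 0.5, the truth is 0.5, the change contrast gives 1 − 0.75 = 0.25, and the direct comparison gives 0.5 − 0.5·1 = 0. The case for it as main analysis is that a crossover with a washout and an 8-week limit already presumes no persistence.

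**Conclusion.** The point holds as a gap in specification that can produce a wrong primary comparison. It is certain that V2 serves both changes and that the plan names no within-child term. The consequences are conditional:

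- **Standard error.** If the two changes are analysed as independent, the type I error is about 11% with equal correlations, 6-8% with decaying correlation, and nominal or below with strong child-specific trends. The plan fixes none of these structures, so neither the size nor the direction is guaranteed.
- **Estimate.** With V3 as the 'after' visit, equal sequences and additive effects, the change contrast runs from 1.5 times A-B (first effect present at V2, gone by V3) to 1.0 times (both persist fully). It understates A's advantage if only A persists and B has some benefit. Pairing does not cure this.

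**What to change.** In Sections 4 and 5:

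1. Name V0, V2 and V3 as the visits for the efficacy comparison, and state the status of the questionnaires handed out at V1.
2. Replace the ANOVA on groups with one within-child crossover model with treatment, period, and either fixed child effects or a free within-child covariance. State that two changes from one child are never treated as independent. A random child intercept on the changes is not enough, because it cannot represent a negative correlation.
3. Under the plan's own washout and 8-week limit, make the V2 and V3 scores the outcomes, with V0 as covariate. With fixed child effects a V0 main effect drops out, so the covariate contributes only in the free-covariance form.
4. Write the no-persistence assumption beside the model. Report the within-child change contrast as a sensitivity analysis, since the direct comparison gives half the true difference if both effects persist.

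The cost is text in two sections and a little more analysis, with no new visits or data. The downside is that the main result then rests openly on a persistence assumption, which the sensitivity analysis probes but does not remove.

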Final Protocol:	June 2019	Clean File:	June 2019
Ethics Approval:	January 2019	Statistical analysis:	
Clinical Phase:		Study Report:	
OBJECTIVES:	To compare the safety and efficacy of administering intravenous autologous cord blood versus personalized noninvasive treatments to children with developmental disorders of the autistic spectrum		
STUDY DESIGN:	An open-label, pilot crossover study over a 12-month period. Participants will be screened and randomized at Visit 0 and at visit V1 will be receiving either intravenous umbilical cord blood or noninvasive treatment. At V2, at 2 months after V1, the other treatment is administered and subsequently the child will be evaluated by questionnaires and child therapist. Parents will report adverse events and complete the M-CHAT, Q-CHAT and CAST questionnaires. Modifications on these questionnaires will be analyzed statistically as a quantitative measure of child's improvement.		
SUBJECTS:	
Inclusion criteria Males and females between 3 and 7 years of age:
 
 • parents informed of the nature of the study and will give written informed consent, • have body weights between 10-30 kg, • have no clinically significant abnormal values on hemoleucogram during screening, • be on no regular medical treatment • have no known allergies to treatments 
Exclusion criteria
 
 • Any genetic or metabolic disease or condition which might compromise the haematopoietic, renal, endocrine, pulmonary, central nervous, cardiovascular, immunological, dermatological, gastrointestinal or any other body system. • History of allergic conditions – asthma, urticaria, eczema. • History of autoimmune disorders 		

	
 • Intake of any medication within 14 days before start of the study • Presence of significant abnormal hemoleucogram results during screening.
TREATMENT TO BE EVALUATED	
Active Treatment A: Autologous umbilical cord blood administered intravenously as single treatment .
 
Active Treatment B: Personalized daily treatment following evaluation with a combination of intranasal Oxytocin; Curcumin; Lecithin, Piracetam, Tecfidera; PQQ; Magnesium citrate and vitamin B6

DURATION OF STUDY	12 months

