1.2 Study Rationale

Even though it is a recent development, UCB has had the best results so far in treating children with ASD and its results recommend it for treatment to any child with ASD and who had UCB collected at birth. Two important questions arise:

- what other treatment can be recommended to the ASD children without UCB collected at birth, and with what comparative efficacy, and
- being a one-time intervention, can we improve/add to UCB infusion other substances which have a very good safety profile (well tolerated) and at least theoretically have a benefit in improving neuronal function?

To begin to answer these questions we have devised an open-label clinical study with a crossover design (all children receive both treatments, albeit in a different sequence).

One important novelty with our study is that the treatment to which UCB is compared is not the same to all children, but is individually tailored to address specifically the most important problems the child has (inflammation, anxiety/social avoidance, myelination, global delay, etc)

Based on the results of the testing with the M-CHAT-R, Q-CHAT and CAST questionnaires and the evaluation from child psychologist, a recommendation for treatment will be made.

The noninvasive treatment consists of a combination of at least two substances from the

following: Oxytocin 10 UI/day intranasally, Magnesium citrate and vitamin B6 ½ cp qd, pironoquinolinquinone (PQQ) 20 mg qd, Lecithin 1000 mg qd, Curcumin 500 mg qd. The specific treatment components will be recommended and administered according to the criteria below, after performing all the tests (imagistics, labs, questionnaires) which can suggest a deficiency on one or more of the following directions:

- inflammatory problem (IP markers on labs, white matter changes, diffuse or no specific modification on MRI)
- myelination (MRI changes),
- anxiety/social avoidance (questionnaires),
- severe developmental delays in cognition, logic, verbalization

1. ***Curcumin 250 mg bid*** will be included in the child's regimen if the imagistics (MRI/CT scan) and/or laboratory values (IP) suggest the presence of an inflammatory status, either in the CNS (white matter modifications on the brain scan) or systemic (abnormal values in the Inflammatory Panel done from blood);

2. ***Oxytocin 10 UI/day*** via intranasal administration will be administered if a social-communication deficit is clearly shown at evaluation

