3. ***Lecithin 500 mg bid*** will be administered if brain imaging reveals any demyelination/myelination deficits, global cerebral atrophy or regional atrophy

4. ***Magnesium citrate with vitamin B6 (150 mg/6 mg qd)*** will be included if restlessness/agitation/anxiety is present significantly in the clinical picture

5. ***Piranoquinolinquinone (PQQ) 20 mg/day*** will be administered in situations of apathic/disinterested behavior, marked introversion, marked developmental delays

6. ***Optional medication for special situations***, with parent's clear understanding, a few other treatment options will be included – ex.

- Tecfidera (dimethyl fumarate) 60 mg bid with food (presence of hypo/demyelination with an autoimmune component); immune modulation is involved in ASD as documented in Kornberg, 2018
- Boswellia extract 400 mg bid – decreases activation of NfK-beta which is the main modulator of both inflammation and neuronal connections
- piracetam (Nootropil) 400 mg bid (presence of severe developmental delays with low motor coordination and energy levels)
- Bacopa monieri (presence of demyelination in absence of immune over-activation)
- Uridine (inflammation mitigation, mitochondrial function stimulation)
- Hipophae rhamnoides oil (source of omega-7 unsaturated fatty acids for synaptic vesicles)

The decision of which of these components should be given is taken after all tests are done and the child psychologist/therapist and the study investigator discuss the case and afterwards discuss the practical issues of administering the recommended treatment with the parents.

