3 STUDY PLAN AND PROCEDURES

3.1 Study design

This is a twelve months long, open-label, crossover study to evaluate the comparative efficacy and safety of UCB versus non-invasive treatments in children with ASD. Each participant will receive both treatments in a random sequence.

The UCB is autologous, previously harvested at the child's birth and cryopreserved in liquid nitrogen for later use.

The UCB infusion was performed at Angiomedica Hospital, [name] as main site and in two additional clinical sites: Medicover Hospital, [name], and Ponderas Academic Hospital, [name], all in Bucharest, Romania by anesthesiologist and pediatric physician, based on the Duke protocol.

Prior to UCB infusion, HLA typing of the child will be performed at the National Institute of Hematology, as well as the HLA typing of the UCB prior to thawing – for positive identification. During this time the UCB collection will be kept in liquid nitrogen for a maximum of 72 hours, after which thawing and preparing of the UCB for infusion will be performed by [name]; the thawing is done in optimal conditions for preserving simultaneously both sterility and viability of the cryogenated cells - the Vita 34 or Rubinstein protocols; testing for viability will be done with Trypan Blue and flowcytometry. Choosing optimal conditions is based upon the minimum number of processing steps necessary (fewest number of centrifugations and shortest time of processing, with best recovery of various stem cells) and ensuring sterility.

The non-invasive treatment combination is prescribed by the study investigator after the three questionnaires are answered and an evaluation by child therapist/psychologist is performed independently. This treatment is

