3.2.1 Inclusion criteria

To be enrolled, the following criteria have to be fulfilled at Visit 2:

1. Children of either sex between 3 and 7 years.
2. Body weight between 15 and 30 kg
3. Diagnosed with ASD
4. No significant diseases or clinically significant abnormal laboratory values during screening
5. On no regular medical treatment

6. Parents able to be informed of the nature of the study and willing to give written informed consent (Consent must be obtained before any study-related procedures are conducted).

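### Eligibility and allocation rules conflict: enrolment criteria are dated to Visit 2, a score-based recommendation is worded as a choice of treatment, and randomisation may precede the eligibility laboratory results

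*Combined protocol and SAP*

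**What the plan says.** **When eligibility is judged.** Section 3.2.1 opens its list with "To be enrolled, the following criteria have to be fulfilled at Visit 2". Section 3.1.1 gives the first treatment at Visit 1 (V1) and puts Visit 2 (V2) 8 weeks later, when the second treatment is given. The synopsis says "Participants will be screened and randomized at Visit 0". Section 4.2 assesses eligibility at Visit 0 (V0) and records eligibility checks before dosing at V1.

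**How the sequence is set.** Section 3.1: "Each participant will receive both treatments in a random sequence". Section 3.3.2: "Each participant will be randomly assigned to begin the study either with the UCB infusion or the non-invasive treatment". Section 3.1.1 places the randomisation at V0. Yet section 4.2, also under V0, says that the M-CHAT-R, Q-CHAT and CAST results and the psychologist's evaluation lead to a step in which "a recommendation for treatment will be made for either UCB administration or the noninvasive treatment for 6 weeks".

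**When laboratory eligibility is known.** Inclusion criterion 4 (3.2.1) and exclusion criterion 7 (3.2.2) rule out children with clinically significant abnormal laboratory results at screening. Section 3.1.1 draws the blood and randomises at the same visit, V0.

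**The concern.** Read literally, section 3.2.1 makes enrolment depend on a child's state after the first treatment, including laboratory values that the treatment could have changed. That is selection on post-treatment status.

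Read literally, the V0 sentence in section 4.2 lets baseline scores steer which treatment comes first. Section 4 uses the same questionnaires as the efficacy measure. A sequence chosen on the baseline score brings regression to the mean into the comparison. The study is open-label, and section 3.3.2 describes no method of generating or concealing the sequence that would rule this out.

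If randomisation happens while blood results are pending, some randomised children may prove ineligible at the V1 check. They would be lost after randomisation, and section 3.2.4 allows removal for incorrect enrolment or randomisation.

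**Working it through.** The first and third items are settled by comparing the texts. The plan gives no figure to reproduce for any of the three.

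**1. Visit 2.**
- First treatment: V1 (3.1.1). Visit 2: V1 + 8 weeks (3.1.1).
- Enrolment criteria: Visit 2 (3.2.1).
- Eligibility assessment: V0 and pre-dose V1 (synopsis, 4.2).

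The 3.2.1 date therefore falls 8 weeks after the event that it should precede. Two details point to a numbering slip. The same list requires consent before any study procedure. And the laboratory text under section 4.4.2 labels blood samples for visits 2 to 5, although the 3.1.1 table schedules blood only at V0, V1 and V2.

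**2. Recommendation against randomisation.** Section 1.2 (Study Rationale) has nearly the same sentence, "and the evaluation from child psychologist, a recommendation for treatment will be made", without the choice of treatment, and goes on to the components of the noninvasive regimen: "The decision of which of these components should be given is taken after all tests are done". Section 3.1 agrees: "The non-invasive treatment combination is prescribed by the study investigator after the three questionnaires are answered". On that reading the effect on allocation is zero.

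To size the literal reading, the following was assumed, since the documents give no correlations or variances:
- Scores at V0, V2 and V3 are standard normal with no treatment effect, and n=25 (5.1).
- Section 4 defines efficacy as the before-after difference for each treatment. With V0 as the first pre-treatment score (3.1.1 table), the contrast is D = (V2−V0) − (V3−V2) = 2·V2 − V0 − V3.
- D is compared between sequences by a two-sided t test at 5%.
- Correlation between visits is r = 0.6, 0.7 or 0.8, either equal for all pairs or decaying (r for adjacent visits, r² for V0-V3).
- Sequence is set either by a mild preference (logistic, slope 1, so the odds multiply by e¹ ≈ 2.7 per SD of V0) or by a median split on V0.

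Given V0, the mean of D is (2r − 1 − r)·V0 = −(1−r)·V0 for equal correlation and (2r − 1 − r²)·V0 = −(1−r)²·V0 for decaying. The mean of the upper half of a standard normal is 0.798. The large-sample bias under a median split (half the between-sequence difference) is therefore:
- equal: 0.798(1−r) = 0.32 / 0.24 / 0.16 SD
- decaying: 0.798(1−r)² = 0.13 / 0.07 / 0.03 SD

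Simulation, 40,000 runs per cell, n=25, for r = 0.6 / 0.7 / 0.8:

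| Allocation | Correlation | Bias (SD) | False positives (%) |
|---|---|---|---|
| Mild preference | decaying | 0.065 / 0.039 / 0.017 | 5.7 / 5.1 / 5.0 |
| Mild preference | equal | 0.164 / 0.125 / 0.082 | 8.0 / 7.2 / 6.5 |
| Median split | decaying | 0.124 / 0.070 / 0.031 | 7.3 / 5.8 / 5.3 |
| Median split | equal | 0.309 / 0.233 / 0.156 | 16.3 / 13.7 / 10.5 |

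Random allocation gave 4.8-5.2% throughout.

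Hand check of the largest cell (equal correlation, r = 0.6): Var(D) = 6 − 6r = 2.4. Within a half, the variance is 2.4 − 0.4² × 0.798² ≈ 2.30, so the SD is about 1.52. The standard error with 12 and 13 children is 1.52 × √(1/12 + 1/13) ≈ 0.61. The difference is 2 × 0.309 = 0.618, about 1.0 standard error. Against a critical t of 2.07 on 23 degrees of freedom, this gives about 16%, as simulated.

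**3. Laboratory timing.** Blood is drawn at V0, randomisation is at V0, and the eligibility check is pre-dose at V1. Nothing makes randomisation wait for the results. Any room to wait depends on the V0-V1 interval, which is stated in three ways: 7-14 days (3.1.1), 14-21 days and longer for UCB preparation (3.3.1), and screening within 14 days before first ingestion (4.2). Only day 14 satisfies all three, and a longer UCB preparation breaks the first and third. No screen-failure or removal rate is given, so the loss cannot be sized.

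**The case against.** The strongest reply is that the intended meaning can be recovered. Four places say that the sequence is random. Section 4.2 refers to section 3.1.1 for the visit schedule, and that section randomises at V0. Every child is to receive both treatments, so a choice of one or the other cannot be meant literally. Enrolment after treatment could not be carried out under this schedule. All of this stands, and it is why the likely effect of the first two items is nil. It does not remove the need to correct them: section 4.2 is the visit-by-visit instruction, its V0 text does not mention randomisation, and section 3.2.1 is the operative eligibility list.

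A reader might infer that the trial allocates by clinical choice, or that children really are enrolled after treatment. The documents do not support either. A reader might also take the note in 4.2 on drawing inflammatory, electrolyte and liver tests at V1 to mean that eligibility bloods can be put off until then. The 3.1.1 table schedules those tests at V0 and only HLA and microbiology at V1, which favours an additional draw. The laboratory-timing point does not need that reading: same-day blood draw and randomisation is enough.

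The simulated figures are hypothetical. No passage suggests a severity cut-off, and the 16% needs deterministic allocation together with equal correlations.

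**Conclusion.** The conflicts are real and should be fixed, as wrong or unclear operative wording rather than as evidence of a non-randomised trial. The Visit 2 date is wrong as written and probably a slip. The recommendation has zero effect under the likely reading. If scores did influence sequence, the false-positive rate for the before-after contrast would be about 5-8% with a mild preference and at most about 16% over the cases tried, against a nominal 5%. These values rest on assumed correlations, normal scores and assumed strength of preference. A direct comparison of V2 and V3 scores would behave differently, but it is not the endpoint that section 4 defines. The randomisation-before-results gap holds without relying on either slip; its size is unknown.

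Two further inferences should not be drawn from this point. The count of children who have received both treatments (3.2) is a recruitment rule and does not define an analysis set. The intention-to-treat wording in 5.2, spelled out only for safety, raises a separate question about the efficacy population and carries no weight here.

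**What to change.** - **3.2.1:** replace the reference to Visit 2 with a requirement that the criteria are met before randomisation.
- **4.2, Visit 0:** state that V0 results determine only the composition of the noninvasive treatment, and that the sequence is set by randomisation alone.
- **3.1.1 and the synopsis:** randomise once the V0 eligibility laboratory results are available, keeping the pre-dose check at V1 as a safeguard.
- **3.1.1, 3.3.1 and 4.2:** reconcile the three V0-V1 windows, and say whether a V1 blood draw replaces or adds to the V0 draw.

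The first two changes are wording only. The third alters the V0 procedure: sequence assignment, and with it the arrangement of UCB release, moves somewhat later. The documents give no laboratory turnaround time, so the delay cannot be sized; it has to fit the reconciled window. No extra visits, tests or children are needed.
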